5.14.3. Clinical Laboratory Assessments

Descriptive summaries of selected (quantitative) clinical laboratory results will be presented by treatment group and study visit. Laboratory values outside the normal range for each systematically collected hematology, blood chemistry, and urinalysis parameter will be identified. Each subject's hematology, blood chemistry, and quantitative urinalysis values will be flagged as "low" (below the lower limit of normal/LLN), "normal" (within the normal range), or "high" (above the upper limit of normal/ULN) relative to the normal ranges of the central laboratory. Each subject's qualitative urinalysis results will be flagged as "normal" or "abnormal." In addition, the severity of laboratory abnormality will be graded based on toxicity criteria specified in Section 9.6 in reference to Common Terminology Criteria for Adverse

Events (CTCAE) Version 5.0. The result of each laboratory test for individual subjects will be presented in a listing with the normal range defined by the central laboratory, the status relative to the normal range, and the toxicity grade.

Shift table will be used to summarize shifts from baseline toxicity grades to greatest (worst) treatment-emergent laboratory toxicity. For hematology and, blood chemistry, and quantitative urinalysis parameters that toxicity grade was not defined, a shift table for each laboratory test will be based on the shift from baseline high/normal/low status to the status of the maximum post-baseline value and the minimum post-baseline value (including test results from unscheduled visits, if any). Similarly, for qualitative urinalysis parameters, shifts from baseline normal/abnormal status to the worst post-baseline status will be summarized.

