Gamma-Glutamyl Transpeptidase will have grades 1-4 and based on ULN only

- Grade 1 being any values from the ULN to 2.5 x ULN,
- Grade 2 from >2.5 to 5.0 x ULN
- Grade 3 from >5.0 to 20.0 x ULN
- Grade 4 from>20.0 x ULN

Lab Test = Glucose

CTCAE Term	Grade 1	Grade 2	Grade 3	Grade 4	Grade 5
Hyperglycemia	Abnormal glucose above baseline with no medical intervention	Change in daily management from baseline for a diabetic; oral antiglycemic agent initiated; workup for diabetes	Insulin therapy initiated; hospitalization indicated	Life-threatening consequences; urgent intervention indicated	Death
Hypoglycemia	<lln -="" 55="" dl;
<lln -="" 3.0="" l<="" mmol="" td=""><55 - 40 mg/dL; <3.0 - 2.2 mmol/L	<40 - 30 mg/dL; <2.2 - 1.7 mmol/L	<30 mg/dL; <1.7 mmol/L; life- threatening consequences; seizures	Death	</lln></lln>	<55 - 40 mg/dL; <3.0 - 2.2 mmol/L	<40 - 30 mg/dL; <2.2 - 1.7 mmol/L	<30 mg/dL; <1.7 mmol/L; life- threatening consequences; seizures	Death

Hypoglycemia will have grades 1-4,

- Grade 1 being any values from the LLN to 55 mg/dL,
- Grade 2 from 40 to <55 mg/dL,
- Grade 3 from 30 to <40 mg/dL,
- Grade 4 <30 mg/dL

Hyperglycemia will have one grade using the WHO criterion below

• Grade 1 >200 mg/dL;

Lab Test = Lipase

CTCAE Term	Grade 1	Grade 2	Grade 3	Grade 4	Grade 5
Serum lipase increased	>ULN - 1.5 x ULN	>1.5 - 2.0 x ULN; >2.0 - 5.0 x ULN and asymptomatic	>2.0 - 5.0 x ULN with signs or symptoms; >5.0 x ULN and asymptomatic	>5.0 x ULN and with signs or symptoms	-

Lipase will have Grades 1, 2 and 3:

- Grade 1 being any values from the ULN to 1.5 x ULN
- Grade 2 from >1.5 to 5.0 x ULN
- Grade 3 from>5 x ULN

Lab Test = Magnesium

CTCAE Term	Grade 1	Grade 2	Grade 3	Grade 4	Grade 5
Hypermagnesemia	>ULN - 3.0 mg/dL; >ULN - 1.23 mmol/L	-	>3.0 - 8.0 mg/dL; >1.23 - 3.30 mmol/L	>8.0 mg/dL; >3.30 mmol/L; life- threatening consequences	Death
Hypomagnesemia	<lln -="" 1.2="" dl;
<lln -="" 0.5="" l<="" mmol="" td=""><1.2 - 0.9 mg/dL; <0.5 - 0.4 mmol/L	<0.9 - 0.7 mg/dL; <0.4 - 0.3 mmol/L	<0.7 mg/dL; <0.3 mmol/L; life- threatening consequences	Death	</lln></lln>	<1.2 - 0.9 mg/dL; <0.5 - 0.4 mmol/L	<0.9 - 0.7 mg/dL; <0.4 - 0.3 mmol/L	<0.7 mg/dL; <0.3 mmol/L; life- threatening consequences	Death

Hypermagnesemia will have grades 1, 3, and 4,

- Grade 1 being any values from the ULN to 3.0 mg/dL,
- Grade 3 from >3.0 to 8.0 mg/dL,
- Grade 4 from>8.0 mg/dL

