Hypomagnesemia will have grades 1 - 4,

- Grade 1 being any values from the LLN to 1.2 mg/dL,
- Grade 2 from 0.9 to <1.2 mg/dL,
- Grade 3 from 0.7 to <0.9 mg/dL,
- Grade 4 <0.7 mg/dL

Lab Test = Potassium

CTCAE Term	Grade 1	Grade 2	Grade 3	Grade 4	Grade 5
Hyperkalemia	>ULN - 5.5 mmol/L	>5.5 - 6.0 mmol/L; intervention initiated	>6.0 - 7.0 mmol/L; hospitalization indicated	>7.0 mmol/L; life- threatening consequences	Death
Hypokalemia	<lln -="" 3.0="" l<="" mmol="" td="">Symptomatic with <lln -
3.0 mmol/L; intervention indicated</lln>	<3.0 - 2.5 mmol/L; hospitalization indicated	<2.5 mmol/L; life- threatening consequences	Death	</lln>	Symptomatic with <lln -
3.0 mmol/L; intervention indicated</lln>	<3.0 - 2.5 mmol/L; hospitalization indicated	<2.5 mmol/L; life- threatening consequences	Death

Hyperkalemia will have grades 1-4,

- Grade 1 being any values from the ULN to 5.5 mmol/L,
- Grade 2 from >5.5 to 6.0 mmol/L,
- Grade 3 from >6.0 to 7.0 mmol/L,
- Grade 4 from>7.0 mmol/L

Hypokalemia will have grades 1, 3, and 4,

- Grade 1 being any values from the LLN to 3.0 mmol/L,
- Grade 3 from >2.5 to 3.0 mmol/L,
- Grade 4 <2.5 mmol/L

Lab Test = Sodium

CTCAE Term	Grade 1	Grade 2	Grade 3	Grade 4	Grade 5
Hypernatremia	>ULN - 150 mmol/L	>150 - 155 mmol/L; intervention initiated	>155 - 160 mmol/L; hospitalization indicated	>160 mmol/L; life- threatening consequences	Death
Hyponatremia	<lln -="" 130="" l<="" mmol="" td="">125-129 mmol/L and asymptomatic	125-129 mmol/L symptomatic; 120-124 mmol/L regardless of symptoms	<120 mmol/L; life- threatening consequences	Death	</lln>	125-129 mmol/L and asymptomatic	125-129 mmol/L symptomatic; 120-124 mmol/L regardless of symptoms	<120 mmol/L; life- threatening consequences	Death

Hypernatremia will have grades 1-4,

- Grade 1 being any values from the ULN to 150 mmol/L,
- Grade 2 from >150 to 155 mmol/L,
- Grade 3 from >155 to 160 mmol/L,
- Grade 4 from>160 mmol/L

Hyponatremia will have grades 1-4,

- Grade 1 being any values from the LLN to 130 mmol/L,
- Grade 2 from 125 to <130 mmol/L,
- Grade 3 from 120 to <125 mmol/L,
- Grade 4 <120 mmol/L

Lab Test = Triglycerides

CTCAE Term	Grade 1	Grade 2	Grade 3	Grade 4	Grade 5
Hypertriglyceridemia	150 mg/dL - 300 mg/dL; 1.71 mmol/L - 3.42 mmol/L	.	>500 mg/dL - 1000 mg/dL; >5.7 mmol/L - 11.4 mmol/L	>1000 mg/dL; >11.4 mmol/L; life- threatening consequences	Death

Triglycerides will have grades 1-4,

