- Grade 1 being any values from the 150 to 300 mg/dL,
- Grade 2 from >300 to 500 mg/dL,
- Grade 3 from >500 to 1000 mg/dL,
- Grade 4 from>1000 mmol/L

Lab Test = Uric Acid

CTCAE Term	Grade 1	Grade 2	Grade 3	Grade 4	Grade 5
Hyperuricemia	>ULN without physiologic consequences	-	>ULN with physiologic consequences	Life-threatening consequences	Death

Uric Acid will not be CTCAE graded.

Lab Test = Bicarbonate or CO2

CTCAE Term	Grade 1	Grade 2	Grade 3	Grade 4	Grade 5
Blood bicarbonate decreased	<lln and="" initiated<="" intervention="" no="" td="">-	-	-	-	</lln>	-	-	-	-

Bicarbonate or CO2 will not be CTCAE graded.

Lab Test = Phosphorus or Phosphate

CTCAE Term	Grade 1	Grade 2	Grade 3	Grade 4	Grade 5
Hypophosphatemia	Laboratory finding only and intervention not indicated	Oral replacement therapy indicated	Severe or medically significant but not immediately life-threatening; hospitalization or prolongation of existing hospitalization indicated	Life-threatening consequences	Death
Hyperphosphatemia	Laboratory finding only and intervention not indicated	Noninvasive intervention indicated	Severe or medically significant but not immediately life-threatening; hospitalization or prolongation of existing hospitalization indicated	Life-threatening consequences; urgent intervention indicated (e.g., dialysis)	Death

Phosphorus or Phosphate will not be CTCAE graded.

Lab Test = Serum pH [This is not urine pH]

CTCAE Term	Grade 1	Grade 2	Grade 3	Grade 4	Grade 5
Acidosis	pH <normal, but
>=7.3</normal,>	-	pH <7.3	Life-threatening consequences	-
Alkalosis	pH >normal, but <=7.5	-	pH >7.5	Life-threatening consequences	-

Serum pH will be graded in both directions with Grades 1 and 3 only.

Acidosis Grade 1 .<LLN, but >=7.3 Grade 3, pH < 7.3

Alkaosis Grade 1 .>ULN, but <=7.5 Grade 3, pH < 7.5

Lab Test = Activated Partial Thromboplastin Time

CTCAE Term	Grade 1	Grade 2	Grade 3	Grade 4	Grade 5
Activated partial thromboplastin time prolonged	>ULN - 1.5 x ULN	>1.5 - 2.5 x ULN	>2.5 x ULN; bleeding	-	-

APTT will be graded in Grade 1-3

- Grade 1 being any values from the >ULN to 1.5 x ULN,
- Grade 2 from >1.5 to 2.5 x ULN,
- Grade 3 from >2.5 x ULN,

Lab Test = International Normalized Ratio

CTCAE Term	Grade 1	Grade 2	Grade 3	Grade 4	Grade 5

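### Most Grade 1 bullets in SAP 9.6 omit the strict sign at the normal limit, so a result exactly at LLN or ULN can be both normal and Grade 1

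*SAP*

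**What the plan says.** SAP 5.14.3 gives each quantitative laboratory result two labels. The first is its status against the central laboratory's range: a result is "flagged as 'low' (below the lower limit of normal/LLN), 'normal' (within the normal range"), or high when it lies above ULN. A result equal to a limit is therefore normal. The second is a toxicity grade, taken from SAP 9.6 with reference to CTCAE version 5.0. Both labels appear in the same listing. For graded tests the shift table runs from the baseline grade to the worst treatment-emergent grade.

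For each test, SAP 9.6 prints the CTCAE row and then the sponsor's own grading bullets. For sodium, the Grade 1 bullets are "Grade 1 being any values from the LLN to 130 mmol/L" on the low side and "Grade 1 being any values from the ULN to 150 mmol/L" on the high side. The CTCAE cell above the high-side bullet reads ">ULN - 150 mmol/L", which excludes the limit. The aPTT bullet keeps the sign: "Grade 1 being any values from the >ULN to 1.5 x ULN".

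**The concern.** The bullets decide the grade. They depart from the CTCAE rows on purpose in several places: liver tests are graded on ULN alone, high glucose uses a WHO cut-off, and platelets are not graded. A programmer would follow them. In the same lists the higher grades mark an excluded end with a sign, as when low-sodium Grade 2 stops short of 130 and high-sodium Grade 2 starts above 150. A bare LLN or ULN is then naturally coded as included.

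The result would be a listing that contradicts itself on one line, and a shift table that counts some in-range values as toxicity, at baseline and after it. Two programmers could also code the rule differently, which matters because SAP 9.7 requires verification by independent programming.

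**Working it through.** No sample-size or power figure is involved, so the check sets the rules side by side and runs boundary values through them.

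**Which bullets are affected.** Among graded tests in protocol Table 9, the bare limit opens Grade 1 for 12 tests: ALP, ALT, AST, bilirubin, calcium, creatinine, low glucose, potassium, sodium, hemoglobin, neutrophils and low WBC. Calcium, potassium and sodium have it in both directions, so the bullets number 9 + 3 × 2 = 15. The CTCAE Grade 1 cell with its strict sign is legible for calcium, creatinine, low glucose, potassium, sodium, hemoglobin, neutrophils and WBC. For ALP, ALT, AST and bilirubin that cell is incomplete in the text available for this review, so for those four the comparison rests on SAP 5.14.3.

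**Which are not.** aPTT, fibrinogen, serum pH and eGFR/CrCl keep strict signs. INR and triglycerides use fixed cut-offs.

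**Boundary values for sodium.** The documents give no limits. Assume LLN 135 and ULN 145 mmol/L.

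| Result (mmol/L) | SAP 5.14.3 status | 9.6 bullet, read literally | CTCAE row in 9.6 |
|---|---|---|---|
| 134 | low | Grade 1 low | Grade 1 low |
| 135 | normal | Grade 1 low | no grade |
| 136 | normal | no grade | no grade |
| 144 | normal | no grade | no grade |
| 145 | normal | Grade 1 high | no grade |
| 146 | high | Grade 1 high | Grade 1 high |

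Assumed limits of 133–144 and 137–147 give the same pattern. The rules disagree only when the result equals a limit. With the strict sign restored, all three agree on whether these values are in range.

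**Hypokalemia in the same list.** The bullets set Grade 1 from LLN down to 3.0, Grade 3 from above 2.5 to 3.0, and Grade 4 below 2.5 mmol/L.

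- A result of 3.0 satisfies both Grade 1 and Grade 3.
- A result of 2.5 is not above 2.5, so it is not Grade 3. It is not below 2.5, so it is not Grade 4.

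The CTCAE row above has neither problem: its Grade 3 runs from below 3.0 down to and including 2.5.

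**Thresholds that do not depend on this wording.** The hematologic AESI and discontinuation limits (Protocol 8.4.6.2) are fixed numbers. The liver AESI rule (Protocol 8.4.6.3) and the SAP 5.14.3 liver table use multiples of ULN with strict signs. Grades 2 to 4 do not start at LLN or ULN.

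**The case against.** The best defence is that the strict rule is already in the SAP. The CTCAE rows exclude the limit, and the abbreviation list (SAP 9.8) defines LLN as under the limit and ULN as above it. The bullets are also visibly shorthand, as hypokalemia shows, so strict logic should not be read into a missing sign. Part of this stands: the SAP does not adopt a settled rule that a value at the limit is a toxicity. But the abbreviation list cannot resolve the matter. SAP 4.1.12 and 5.14.3 use LLN and ULN as the limits themselves, and a multiple of ULN has no meaning otherwise. What remains is a conflict within 9.6, and between 9.6 and 5.14.3.

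A reader might infer two stronger points.

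**That extra Grade 1 results dilute a difference between arms.** This is not supported in general. As an illustration, assume sodium reported in whole mmol/L, range 135–145, mean 140, SD 2.5, within-subject correlation 0.5, three post-baseline samples, and a mean lower by 0.8 in one arm. Low-sodium Grade 1 or worse is then 3.6% against 7.4% under the strict rule, and 8.8% against 15.9% under the literal one.

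- Ratio: 7.4/3.6 = 2.1 falls to 15.9/8.8 = 1.8.
- Difference: 7.4 − 3.6 = 3.8 points rises to 15.9 − 8.8 = 7.1 points.
- SE with 50 per arm, √[p₁(1−p₁)/50 + p₂(1−p₂)/50]: 0.0454, then 0.0654.
- Difference/SE: 0.038/0.0454 = 0.84 rises to 0.071/0.0654 = 1.09.

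Dilution appears only on the ratio scale, and every input is assumed.

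**That the glucose grading is an error.** SAP 9.6 says "Hyperglycemia will have one grade using the WHO criterion below", namely above 200 mg/dL. SAP 5.14.3 limits the other format, in which "a shift table for each laboratory test will be based on the shift from baseline high/normal/low status", to tests without a defined grade. A rise from normal to between ULN and 200 mg/dL therefore shows in no shift table. That gap is real. But such values are still flagged high in listings and enter the summaries by visit, with third quartile and maximum. The printed CTCAE hyperglycemia grades depend on clinical management and cannot be derived from a laboratory value alone. An extra table is a preference.

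**Conclusion.** The point holds as a minor specification error. In 15 Grade 1 bullets covering 12 in-panel tests, SAP 9.6 lacks the sign needed to agree with SAP 5.14.3 and with the legible CTCAE rows. Literal coding would label a result exactly at a limit both normal and Grade 1. The hypokalemia bullets contain one overlap (3.0 mmol/L) and one gap (2.5 mmol/L).

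The consequence is limited to Grade 1 and to results equal to a limit, and the rule is the same in all arms. Laboratory summaries are descriptive (Protocol 9.4.2). How many subjects would be affected depends on the central laboratory's ranges, reporting precision and variability, none of which is in the documents, so no figure is given. The conclusion assumes that the bullets, rather than the rows, would be programmed.

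**What to change.** In the Grade 1 bullets of SAP 9.6 for the 12 tests listed, write <LLN to the lower cut-off or >ULN to the upper cut-off. Make the same edit for tests outside the protocol panel that share the wording, such as albumin, amylase and magnesium. Restate the hypokalemia bullets to match the CTCAE row above them: Grade 1 <LLN to 3.0, Grade 3 from 2.5 to <3.0, Grade 4 <2.5 mmol/L. It would also help to correct the LLN and ULN entries in SAP 9.8 so that they name the limits themselves.

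A high/normal/low shift table for glucose is optional.

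The cost is a short text edit and one comparison operator per bullet in the grading program, before database lock. No data collection or subject is affected.

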## 2.3 Benefit/Risk Assessment

There are no important identified risks for CVL-865. Fetal toxicity, bone marrow suppression and decrease in peripheral hematologic parameters are important potential risks; however, these risks will be minimized during the study by monitoring of hematologic parameters and requiring the use of appropriate contraception and regular pregnancy testing.

Results from a recently completed Phase 2a trial using a photosensitivity model as a proof-of-concept for CVL-865 demonstrated highly robust efficacy. This was shown by a marked and statistically significant mean reduction in standardized photosensitivity ranges to intermittent photic stimulations for single doses of 17.5 mg and 52.5 mg CVL-865 compared with placebo, which was similar to lorazepam 2 mg active control.

Based on available safety and efficacy data for CVL-865, the benefit-risk profile is favorable.

In response to the COVID-19 pandemic, Cerevel has performed a risk assessment of this trial and the investigator of each individual trial site and has implemented measures throughout the protocol, which prioritizes trial participant safety and data validity.

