INR increased	>1.2 - 1.5; >1 - 1.5 x baseline if on anticoagulation; monitoring only indicated	>1.5 - 2.5; >1.5 - 2.5 x baseline if on anticoagulation; dose adjustment indicated	>2.5; >2.5 x baseline if on anticoagulation; bleeding	-	-

INR will be graded in Grade 1-3 without baseline factor

- Grade 1 being any values from the >1.2 to 1.5,
- Grade 2 from >1.5 to 2.5,
- Grade 3 from >2.5,

Lab Test = Eosinophils

CTCAE Term	Grade 1	Grade 2	Grade 3	Grade 4	Grade 5
Eosinophilia	>ULN and >Baseline	-	Steroids initiated	-	-

Eosinophils will not be CTCAE graded

Lab Test = Hemoglobin

CTCAE Term	Grade 1	Grade 2	Grade 3	Grade 4	Grade 5
Anemia	Hemoglobin (Hgb) <lln -="" 10.0="" dl;
<lln -="" 6.2="" l;
<lln -="" 100="" g="" l<="" td="">Hgb <10.0 - 8.0 g/dL; <6.2 - 4.9 mmol/L; <100 - 80g/L	Hgb <8.0 g/dL; <4.9 mmol/L; <80 g/L; transfusion indicated	Life-threatening consequences; urgent intervention indicated	Death	</lln></lln></lln>	Hgb <10.0 - 8.0 g/dL; <6.2 - 4.9 mmol/L; <100 - 80g/L	Hgb <8.0 g/dL; <4.9 mmol/L; <80 g/L; transfusion indicated	Life-threatening consequences; urgent intervention indicated	Death
Hemoglobin Increased	Increase in > 0-2	Increase in >2-4g/dL	Increase > 4 g/DL	-	Death

Decreased Hemoglobin will have grades 1-3, with

- Grade 1 being any values from the LLN to 10 g/DL,
- Grade 2 from 8 to < 10 g/DL and
- Grade 3 < 8 g/DL

Increased Hemoglobin will not be graded.

Lab Test = CD4 Lymphocytes

CTCAE Term	Grade 1	Grade 2	Grade 3	Grade 4	Grade 5
CD4 lymphocytes decreased	<lln -="" 500="" mm3;
<lln -="" 0.5="" 10e9
/L</lln></lln>	<500 - 200/mm3; <0.5 - 0.2 x 10e9 /L	<200 - 50/mm3; <0.2 x 0.05 - 10e9 /L	<50/mm3; <0.05 x 10e9 /L	-

Decreased CD4 count will have grades 1-4, with

- Grade 1 being any values from the LLN to 500/mm3,
- Grade 2 from <500 to 200/mm3 and
- Grade 3 from <200 to 50/mm3 and
- Grade 4 <50/mm3

Lab Test = Lymphocytes

CTCAE Term	Grade 1	Grade 2	Grade 3	Grade 4	Grade 5
Lymphocyte count decreased	<lln -="" 800="" mm3;
<lln -="" 0.8="" 10e9="" l<="" td="" x=""><800 - 500/mm3; <0.8 - 0.5 x 10e9 /L	<500 - 200/mm3; <0.5 - 0.2 x 10e9 /L	<200/mm3; <0.2 x 10e9 /L	Lymphocyte count decreased	</lln></lln>	<800 - 500/mm3; <0.8 - 0.5 x 10e9 /L	<500 - 200/mm3; <0.5 - 0.2 x 10e9 /L	<200/mm3; <0.2 x 10e9 /L	Lymphocyte count decreased
Lymphocyte count increased	-	>4000/mm3 - 20,000/mm3	>20,000/mm3	-	Lymphocyte count increased

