Decreased Lymphocytes will have grades 1-4, with

- Grade 1 being any values from the LLN to 800/mm3,
- Grade 2 from <800 to 500/mm3 and
- Grade 3 from <500 to 200/mm3 and
- Grade 4 <200/mm3

Increase Lymphocytes will have grades 2 and 3 only, with

- Grade 2 from >4000 to 20,000/mm3 and
- Grade 3 >20,000/mm3

Lab Test = Neutrophils

CTCAE Term	Grade 1	Grade 2	Grade 3	Grade 4	Grade 5
Neutrophil count decreased	<lln -="" 1500="" mm3;
<lln -="" 1.5="" 10e9
/L</lln></lln>	<1500 - 1000/mm3; <1.5 - 1.0 x 10e9 /L	<1000 - 500/mm3; <1.0 - 0.5 x 10e9 /L	<500/mm3; <0.5 x 10e9 /L	-

Neutrophils will have grades 1-4, with

- Grade 1 being any values from the LLN to 1500/mm3,
- Grade 2 from 1000 to <1500/mm3 and
- Grade 3 from 500 to <1000/mm3 and
- Grade 4 <500/mm3

Lab Test = Platelets

CTCAE Term	Grade 1	Grade 2	Grade 3	Grade 4	Grade 5
Platelet count decreased	<lln -
75,000/mm3; <lln - 75.0 x 10e9 /L</lln </lln>	<75,000 - 50,000/mm3; <75.0 - 50.0 x 10e9 /L	<50,000 - 25,000/mm3; <50.0 - 25.0 x 10e9 /L	<25,000/mm3; <25.0 x 10e9 /L	-

Platelet count will not be CTCAE graded

Lab Test = WBC

CTCAE Term	Grade 1	Grade 2	Grade 3	Grade 4	Grade 5
White blood cell decreased	<lln -="" 3000="" mm3;
<lln -="" 10e9
/L</lln></lln>	<3000 - 2000/mm3; <3.0 - 2.0 x 10e9 /L	<2000 - 1000/mm3; <2.0 - 1.0 x 10e9 /L	<1000/mm3; <1.0 x 10e9 /L	-
Leukocytosis	-	-	>100,000/mm3	Clinical manifestations of leucostasis; urgent intervention indicated	Death

Decreased WBC will have grades 1-4, with

- Grade 1 being any values from the LLN to 3000/mm3,
- Grade 2 from 2000 to <3,000/mm3 and
- Grade 3 from 1000 to <2,000/mm3 and
- Grade 4 <1000/mm3

High WBC will have grade 1, with

• Grade 1 >11,000/mm3 (https://www.aafp.org/afp/2000/1101/p2053.html),

Lab Test = Urine Glucose

CTCAE Term	Grade 1	Grade 2	Grade 3	Grade 4	Grade 5
Glucosuria	Present	-	-	-	-

Urine Glucose will have grades 1,

• Grade 1 if not negative or trace

Lab Test = Urine Protein

CTCAE Term	Grade 1	Grade 2	Grade 3	Grade 4	Grade 5
Proteinuria	1+ proteinuria; urinary protein ≥ULN - <1.0 g/24 hrs	Adult: 2+ and 3+ proteinuria; urinary protein 1.0 - <3.5 g/24 hrs; Pediatric: Urine P/C (Protein/Creatinine) ratio 0.5 - 1.9	Adult: Urinary protein >=3.5 g/24 hrs; 4+ proteinuria; Pediatric: Urine P/C (Protein/Creatinine) ratio >1.9	-	-

Urine Protein will have grades 1-3, with

- Grade 1 =1+,
- Grade 2 = 2+ to 3+
- Grade 3 = 4+

Lab Test: Urine RBCs/Blood

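### Platelets are the only one of the four hematologic AESI tests without a worst-grade shift table, although the SAP prints the cut-points

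*SAP*

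**What the plan says.** Protocol 2.3 states that "bone marrow suppression and decrease in peripheral hematologic parameters are important potential risks" and relies on monitoring of blood counts to limit them. Protocol 8.4.6.2 names four tests for this purpose: hemoglobin, WBC, neutrophils and platelets. For platelets, a count below 150 x 10^9/L is a reportable AESI, and a count below 100 x 10^9/L requires study drug to be stopped.

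SAP 5.14.3 provides two kinds of laboratory shift table. For graded tests, "Shift table will be used to summarize shifts from baseline toxicity grades to greatest (worst) treatment-emergent laboratory toxicity". For tests with no defined grade, the table runs from baseline high/normal/low status to the status of the highest and lowest post-baseline values.

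SAP 9.6 decides which tests are graded:
- Hemoglobin: "Decreased Hemoglobin will have grades 1-3, with" cut-points listed.
- Lymphocytes: "Decreased Lymphocytes will have grades 1-4, with" cut-points listed.
- Neutrophils: "Neutrophils will have grades 1-4, with" cut-points listed.
- WBC: "Decreased WBC will have grades 1-4, with" cut-points listed.
- Platelets: the CTCAE row is printed with numeric bands throughout (Grade 2, for example, is "<75,000 - 50,000/mm3; <75.0 - 50.0 x 10e9 /L"), followed by "Platelet count will not be CTCAE graded".

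**The concern.** Platelet count is one of the four blood tests through which the protocol watches for marrow suppression, and it is the only one of them without a severity scale in the analysis. The omission does not follow the appendix's own pattern. The other tests left wholly ungraded (uric acid, bicarbonate, phosphorus, eosinophils, urine blood) have CTCAE rows that depend at least partly on symptoms, consequences or interventions, so a laboratory value alone cannot grade them. The platelet row is purely numeric.

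At stake is a by-arm safety display. For hemoglobin, WBC and neutrophils a reader will see how many subjects in each dose group reached each grade. For platelets the same reader will see only how many became low.

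**Working it through.** The point depends on no sample size, power or error rate, so there is no planned figure to reproduce. The check classifies example platelet counts under three rules.

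**Inputs**
- SAP 5.14.3 rule for ungraded tests: low if the count is below the laboratory LLN.
- SAP 9.6 printed bands (x 10^9/L): Grade 1 from below LLN down to 75; Grade 2 below 75 to 50; Grade 3 below 50 to 25; Grade 4 below 25.
- Protocol 8.4.6.2 limits: below 150 and below 100 x 10^9/L.
- Assumption: the documents do not give the central laboratory's LLN for platelets, so it was set at 130, 140 and 150 x 10^9/L.

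**Results**

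| Lowest count (x 10^9/L) | Status at LLN 130 / 140 / 150 | Printed band | Lowest protocol limit crossed |
|---|---|---|---|
| 145 | normal / normal / low | none / none / Grade 1 | 150 |
| 125 | low / low / low | Grade 1 | 150 |
| 99 | low / low / low | Grade 1 | 100 |
| 80 | low / low / low | Grade 1 | 100 |
| 74 | low / low / low | Grade 2 | 100 |
| 49 | low / low / low | Grade 3 | 100 |
| 24 | low / low / low | Grade 4 | 100 |

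**Reading the table**
1. From 125 down to 24 the current rule gives one category at every assumed LLN. The printed bands give four.
2. Exclusion criterion 14 in Protocol 5.2 bars subjects with platelets below 150 x 10^9/L at Screening, so few should start low. Nearly every fall below the LLN will therefore sit in the single cell from normal to low.
3. The counts 125, 99 and 80 are all Grade 1, because 75 < 100 < LLN for any assumed LLN. Grading alone would not show who crossed the protocol's 100 x 10^9/L limit.
4. Of the four hematologic AESI tests, three are graded and one is not.

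**The case against.** The strongest reply is that a serious platelet fall would not be missed. SAP 5.14.1 summarizes AESIs, AESIs that did not lead to stopping study drug, and events that did. Since a count below 100 x 10^9/L requires stopping and a count from 100 to below 150 requires only reporting and follow-up, these summaries separate the two protocol levels indirectly. SAP 5.14.3 adds descriptive statistics by arm and visit, which include the minimum, and a listing of every value. A reader might infer that a deep fall would go unseen, or that the AESI outputs merge the two limits completely. The documents support neither. Nor do they say that worst-grade shifts are the principal means of detecting the risk.

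What remains is narrower. The split by discontinuation is imperfect, since a subject may stop for another reason, and it cannot tell 99 from 24 x 10^9/L, because both require stopping. Adverse event intensity (Protocol 10.3.3) is rated by discomfort and interference with daily activities, so a deep fall without symptoms could be rated mild. A by-visit minimum shows one extreme value, not a number of subjects. Listings show individual counts without a by-arm tally.

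It is also fair to say that grading adds information only below 75 x 10^9/L, where study drug must already have been stopped. That is a reason for the additional counts at 150 and 100, not for leaving the grades out.

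SAP 9.6 also sets grades for amylase, lipase, CD4 and fibrinogen, which are not in the laboratory panel of Protocol 10.2. A reader might infer that these were given priority over platelets, but the entries may equally be unused standard text, and the point does not rest on them.

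**Conclusion.** The point holds for the shift table and no further. Platelets are the only one of the four hematologic AESI tests without a worst-grade shift table, the SAP gives no reason, and the cut-points are already on the page. With an assumed LLN of 130 to 150 x 10^9/L, falls to 125 and to 24 x 10^9/L are tabulated alike, where the printed bands would separate Grade 1 from Grade 4. An example such as a fall from 200 to 145 should not be used: 145 is low only if the LLN is above 145, which the documents do not establish.

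No efficacy result, error rate or subject-level safety action depends on this. It is a free improvement of low severity.

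**What to change.** In SAP 9.6, replace the sentence that excludes platelets from grading with the four numeric bands already printed there, and include platelets in the worst-grade shift table of SAP 5.14.3.

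Also add a table, by arm, of the number and percentage of subjects whose worst post-baseline platelet count, including unscheduled tests, is below 150 and below 100 x 10^9/L. These are the protocol's existing limits, and the grades do not cut at 100.

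The data are already collected, so the cost is minor programming before database lock. Only the presentation changes; no clinical threshold does.
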